APPENDIX F ACTION PLAN FOR TREATMENT OF WORSENING OF DISEASE:

Criteria for disease worsening in a clinical trial, by which patients could be termed treatment failures and offered alternative therapies, were preliminarily defined at an IMACS Workshop. These criteria will be incorporated into this trial.

. In order to be classified as “worsening” in this trial subjects will have to meet the following criteria:

(1) Physician global worsening of ≥ 2 cm on the 10 cm visual analog scale (VAS) and a worsening of the manual muscle testing by $\geq 20\%$, or

(2) Global extra muscular organ disease activity (a composite of constitutional, cutaneous, skeletal, gastrointestinal, pulmonary and cardiac activity) worsening by ≥ 2 cm on a 10 cm VAS, or

(3) 3 of any 6 IMACS core set activity measures worse by $\geq 30\%$. And

(4) Subjects will have to meet the above criteria and be classified by the investigator as at least moderately clinically worse.

Patients who improve by less than 5% in at least 3 of 6 core set measures by week 12, will be considered to be not improved : These patients may be offered higher dose therapy at 212 mg (87.5 + 125 mg) for subjects with body weight ≥ 50 kg or 137.5 mg for subjects with body weight < 50 kg abatacept weekly.

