Study Schema: Drugs / Doses / Length of Treatment)	
Study participation will consist of a screening visit and 5 protocol visits over six months (week 0, week 6, week 12, week 18, and week 24) for each subject, and phone follow-up (week 2, week 4, week 8, week 10, week 14, week 16, week 20, and week 22). At Visit 1, which will be treatment initiation, eligible subjects will be instructed on the use and side effects of subcutaneous abatacept and will be started on the study drug (abatacept 125 mg SQ weekly for subjects with body weight \geq 50 KG or abatacept 87.5mg SQ for subjects with body weight < 50 KG).
 
For patients not improving with therapy by at least 5% on at least 3 of 6 core set measures at week 12 and who are clinically unchanged or worse by physician assessment, they would be offered the opportunity to increase their dose of treatment to abatacept 212.5 mg (87.5 + 125 mg) for subjects with body weight \geq 50 kg or to abatacept 137.5 mg (87.5 mg + 50 mg) once a week subcutaneously for subjects with body weight < 50 kg, or to continue on their present dose.
 
An open label extension of 6 months will be offered to subjects who met improvement criteria and are rated as at least minimally improved by physician assessment.

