3.0 STUDY DESIGN

TREATMENT PHASE

This study will employ an open label nonrandomized design in the treatment of subjects with JDM. Study participation will consist of a screening visit and 5 protocol visits over six months (week 0, week 6, week 12, week 18, and week 24) for each subject, and phone follow-up in between in-person visits (week 2, week 4, week 8, week 10, week 14, week 16, week 20, and week 22). Some patients will undergo some of the screening tests at home, and present results at a screening visit. This will enable them to move to the week 0 visit simultaneously and begin treatment.

At Visit 1, which will be treatment initiation, eligible subjects will be instructed on the use and side effects of subcutaneous abatacept. Patients will be started on the study drug (abatacept) 125 mg SQ weekly for subjects with body weight \geq 50KG and 87.5 mg SQ for subjects with weight <50 KG. For patients not improving with therapy by at least 5% on

at least 3 of 6 core set measures (IMACS or PRINTO measures) at week 12, they would be offered the opportunity to increase their dose of treatment to abatacept 212.5 mg SQ weekly (125 mg prefilled syringe plus 87.5 mg prefilled syringe) for subjects with weight \geq 50KG and 137.5 mg SQ weekly (87.5 mg prefilled syringe plus 50 mg prefilled syringe) for subjects with weight <50KG, or to continue on their present dose.

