6.2 Study Medication Schedule

At Visit 1 (week 0), eligible subjects will be instructed on the use and potential side effects of subcutaneous abatacept and will be started on the study drug (abatacept 125 mg SQ weekly for subjects with body weight ≥ 50 , or abatacept 87.5 mg SQ weekly for subjects with body weight < 50 kg). Subjects will be on weekly Abatacept for the duration of the study (from week 0 through week 24). For patients not improving with therapy by at least 5% on at least 3 of 6 core set measures at week 12 (visit 3), and rated as unchanged or worsened from visit 1 by the study physician, they would be offered the opportunity to increase their dose of treatment to abatacept 212.5 mg (125 mg prefilled syringe plus 87.5 mg prefilled syringe) weekly subcutaneously for subjects with body weight ≥ 50 kg or to abatacept 137.5 mg (87.5 mg prefilled syringe plus 50 mg prefilled syringe) for subjects with body weight < 50 kg, or to continue on their present dose.

STUDY SCHEMATIC

The short lines indicate phone follow-ups, which will occur at weeks 2, 4, 8, 10, 14, 16, 20 and 22

An open label extension phase will be offered for up to 6 months (visit could be in time less than that) for patients meeting the definition of improvement and who are rated by their study physician as at least minimally improved.

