- Administer dose of study medication and observe after the injection for at least 15 minutes
- Schedule and instruct the subject to return for the next visit

Phone follow-up #3 (14 days (+/- 7 days after visit 2))

- Adverse events will be reviewed and recorded (NCI Common Toxicity criteria version 4.0).

Phone follow-up #4 (will occur 28 days (+/- 7 days) after visit 2.)

- Adverse event will be reviewed and recorded.

Visit 3 (week 12) will occur 42 days (+/- 10) days after Visit 2

- Review concomitant medication and query for adverse events and document in CRF.
- NCI Common Toxicity Assessment
- Obtain vital signs (HR,BP,RR, oral temperature and weight) and if indicated , by history of shortness of breath or lung disease, pulse oximetry)
- Medical history and perform a full physical examination
- Collect urine sample for pregnancy test for females of child bearing potential prior to administration of study medication (where applicable)
- Core set activity measures: physician global activity, patient/parent global activity, manual muscle testing (MMT-8), CMAS, HAQ/CHAQ, MDAAT, muscle enzymes, CHQ PF-50/SF- 36, and Disease activity score (DAS), physician global damage (VAS)
- Quality of life questionnaires: CHQ PF-50/SF- 36,DLQI , PROMIS/fatigue and Peds QL fatigue
- Physician and patient/parent assessment of study outcome
- Dermatology assessment performed by Rheumatologist : CDASI, photographs of skin rashes, periungual nailfold capillary assessment Dermatology Assessment Performed by Derm: CDASI, MD Global Skin Activity + Damage (Optional)

- Obtain blood samples for Chem-20, GGT, CK, aldolase, LDH, CBC with diff., von Willebrand Factor antigen level, Lymphocyte flow cytometry (TBNK cells) [**may be performed at home institution, up to 10 days before the visit date**]
- Urinalysis
- Collect research blood samples for Immunophenotyping (T, B cells and macrophages), gene expression and cytokine/chemokine analysis (see Section 3.1.h)
- Review if patient improved by $\geq 5\%$ in at least 3 of 6 core set measures (by IMACS or PRINTO measures). If patient did not meet this criterion and was rated by the study physician as unchanged or worsened since visit 1, an option to increase the dose to 212 mg (87.5 + 125 mg) SQ weekly for subjects with body weight ≥ 50 kg or to increase the dose to 137.5 mg (87.5 mg + 50 mg) for subjects with body weight < 50 kg will be presented.

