8.0 DOSE MODIFICATION

The dose of abatacept will remain constant until week 12. For patients not improving with therapy by at least 5% on at least 3 of 6 core set measures at week 12, they would be offered the opportunity to increase their dose of treatment to abatacept 212 mg (87.5 + 125 mg) for subjects with body weight \geq 50 kg or to abatacept 137.5 mg (87.5 mg+ 50 mg for subjects with body weight of < 50 kg) weekly subcutaneously, or to continue on their present dose.

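### The protocol states the week-12 dose-increase trigger inconsistently: five places require a rating of unchanged or worse, three omit it, and Appendix F's count read literally differs from the Visit 3 instruction

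*Combined protocol and SAP*

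**What the plan says.** Eight places in the combined protocol and SAP state who may be offered the higher dose at week 12.

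Five require a rating of unchanged or worse as well as a lack of improvement in the core set measures. The Synopsis (Study Schema) limits the offer to patients not improving on the "core set measures at week 12 and who are clinically unchanged or worse by physician assessment". Section 6.2 adds "and rated as unchanged or worsened from visit 1 by the study physician". Section 7.1, Visit 3, first asks about improvement of at least 5% "in at least 3 of 6 core set measures (by IMACS or PRINTO measures). If patient did not meet this criterion", and then makes both conditions explicit: "If patient did not meet this criterion and was rated by the study physician as unchanged or worsened since visit 1". Section 6.3 and Appendix E Table 1 also include the rating, although the table does not name the rater.

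Three give no rating. Section 3.0 reads "at least 3 of 6 core set measures (IMACS or PRINTO measures) at week 12, they would be offered the opportunity to increase their dose". Section 8.0, the Dose Modification section, refers only to the "core set measures at week 12, they would be offered the opportunity to increase their dose of treatment to abatacept 212 mg". Appendix F puts it thus: "improve by less than 5% in at least 3 of 6 core set measures by week 12, will be considered to be not improved"; it adds that these patients may be offered the higher dose.

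Appendix F does contain a rating: "Subjects will have to meet the above criteria and be classified by the investigator as at least moderately clinically worse". That is item (4) of the definition of disease worsening. The sentence on patients who are not improved comes after it and stands apart.

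**The concern.** Which patients may move to the higher dose in weeks 12 to 24, before the week-24 primary endpoint, depends on which section is followed. No section is said to prevail over the others. The same offer could therefore comply with Section 8.0 and deviate from Section 7.1.

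Two things could differ: whether a patient rated as improved can be offered the increase, and whether a patient with exactly three of six measures improved by at least 5% can be. Eligibility affects exposure, the week-24 PK sample and the safety data. Section 1.3.2 gives 200 mg weekly as the highest dose tested in adults, and the increased dose printed for patients of 50 kg or more is above that figure. No view is taken on the dose or on which rule is right. The point is only that eligibility should have one definition.

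**Working it through.** The plan states no figure to reproduce, so the check sets the passages side by side and then counts logical cases.

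**Step 1. Tally.**

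| Place | Count of measures | Unchanged-or-worse rating | Increased dose printed, ≥50 kg |
|---|---|---|---|
| Synopsis | wording open to two readings | required | 212.5 mg |
| Section 3.0 | same wording; IMACS or PRINTO | not stated | 212.5 mg |
| Section 6.2 | same wording | required | 212.5 mg |
| Section 6.3 | none given | required | no total |
| Section 7.1, Visit 3 | fewer than 3 of 6 improved ≥5%; IMACS or PRINTO | required | 212 mg |
| Section 8.0 | same wording as Synopsis | not stated | 212 mg |
| Appendix E Table 1 | none given; ≤5% by DOI | required, rater not named | none |
| Appendix F | literally, at least 3 of 6 improved <5% | not stated | 212 mg |

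The rating is required in 5 places and absent from 3.

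**Step 2. Count.** Let k be the number of the same six measures improved by at least 5%.

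- Visit 3: criterion not met when k < 3, so k = 0, 1 or 2.
- Appendix F, literal: 6 − k ≥ 3, so k = 0, 1, 2 or 3.

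They differ only at k = 3. The definition of improvement (DOI, Appendix D1) needs at least three measures improved by 20% or more, so k ≥ 3. On the same six measures, a patient who meets the DOI on exactly three, with the other three improved by less than 5%, is not improved under Appendix F read literally but has met the Visit 3 criterion.

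**Step 3. Count and rating together.** Seven values of k times two ratings (unchanged or worse; improved) gives 7 × 2 = 14 cells. Cells in which the offer is open:

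- Visit 3: k ≤ 2 with the rating = 3.
- Appendix F: k ≤ 3, any rating = 4 × 2 = 8 if literal; k ≤ 2, any rating = 3 × 2 = 6 if it only paraphrases Visit 3.
- Synopsis and Section 6.2: 3 or 4, depending on the reading.
- Sections 3.0 and 8.0: 6 or 8, depending on the reading.

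Appendix F differs from Visit 3 in 8 − 3 = 5 cells if literal and 6 − 3 = 3 if a paraphrase.

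**Step 4. All readings.** Three groups of passages (Synopsis with 6.2; 3.0 with 8.0; Appendix F), each with two readings, give 2 × 2 × 2 = 8 combinations. The passages fail to agree in 3 cells in one combination, 4 in one, and 5 in six. If the shared wording is read the same way wherever it occurs, four combinations remain: 3 cells in one and 5 in three. Three cells conflict in every combination: k = 0, 1 or 2 with a rating of improved.

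Section 6.3 and Appendix E Table 1 give no count and are outside this enumeration. Both require the rating, so they do not remove the three common cells.

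**Step 5. Smaller items.** The syringes listed sum to 87.5 + 125 = 212.5 mg, against 212 mg in three places. By Appendix C the IMACS and PRINTO sets differ in at least 1 of 6 measures (muscle enzyme against quality of life) and in up to 3 if CMAS and DAS are used. Sections 3.0 and 7.1 do not say which set governs if the two give different answers.

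**The case against.** The strongest reply is that the working instructions agree. Sections 6.2, 6.3, 7.1 and Appendix E Table 1, which staff use at the visit and at dispensing, all require the rating, and Visit 3 states the count clearly. Appendix F read literally can label a DOI responder as not improved, which suggests that it is loose shorthand for Visit 3. Its permissive wording also leaves room for a condition stated elsewhere. The increase is optional, and nothing in Section 15.0 uses the trigger.

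Much of this stands. The count conflict is less certain than the rating conflict. The four-cell result arises only if identical wording is read two ways. Of the three common cells, no measures improved with a rating of improved is unlikely, because physician global activity is itself one of the six measures. The reference to the DOI in Appendix E may be meant to carry the 3-of-6 structure. Naming IMACS or PRINTO may simply mean that either set suffices. The 212 mg figure looks like a truncation, since the syringe strengths are printed beside it.

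None of this removes the rating conflict. Sections 3.0 and 8.0 say the increase would be offered, without the rating, and no order of precedence is given.

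**Conclusion.** The inconsistency is real and should be fixed. The rating is required in five places and missing from three, including the Dose Modification section, and this needs no interpretation. It alone leaves 3 of 14 logical cases in conflict under every reading. The count conflict raises the disagreement between Appendix F and Visit 3 to 5 cases, provided that Appendix F is read literally and the same six measures are used.

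The cases are not patient shares, and the documents offer no basis for converting them. The consequence is limited: under the intention-to-treat analysis in Section 15.0 every patient counts toward 6 of 10 whichever reading is used. What stays unsettled is who qualifies for the higher dose in weeks 12 to 24.

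**What to change.** Reconcile the Synopsis, Sections 3.0, 6.2, 6.3, 7.1 (Visit 3) and 8.0, Appendix E Table 1 and Appendix F to one trigger. It should fix the count of measures, the inequality at 5%, the measure set that governs, whether the rating is required, and who gives it. Print one figure for the increased dose. The clinical team should decide the content; no rule or dose is proposed here.

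The cost is one protocol wording amendment. No new data are needed, because the week-12 core set measures and the study-outcome rating are already collected (Section 7.1 Visit 3, Section 14.0, Appendix E Table 1).

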APPENDIX G CLINICAL LABORATORY EVALUATIONS

HEMATOLOGY	SERUM CHEMISTRY	URINALYSIS

Total white blood cell count
 
Differential:
 
 Neutrophils Lymphocytes Monocytes Eosinophils Basophils 
Hematocrit
 
Hemoglobin
 
Platelet Count
 
Lymphocyte phenotyping/peripheral (TBNK by flow cytometry)
 
Von Willebrand Factor antigen
	
Electrolytes:
 
 Bicarbonate Chloride Potassium Sodium Calcium Magnesium Phosphorus (inorganic) 
Enzymes:
 
 Aldolase Aspartate aminotransferase (AST) Alanine aminotransferase (ALT) LDH CPK GGT CPK 
Other:
 
 BUN Creatinine QIG panel (IGM, IGG) Hepatitis B surface antigen Hepatitis C antibody TSH HIV Quantiferon Gold ANA/ENA 	
pH
 
Blood
 
Glucose
 
Protein
 
Ketones
 
Nitrites
 
Bilirubin
 
Urobilinogen
 
Leukocyte esterase
 
Microscopic exam if dipstick positive
 
Urine Pregnancy

	MSA/MAA Immunogenicity (HAHA) pK	
--	--	--

Laboratory test results will be reviewed by the Investigator or Sub-Investigator as they become available. The Investigator or Sub-Investigator must determine the clinical significance of all out-of- range laboratory values. Possibly drug-related or clinically relevant abnormal values of uncertain causality must be repeated. Any abnormal values that persist should be followed at the discretion of the Investigator.

